Data analysis:	Propensity scores will be calculated using the listed covariates (below) and used to construct PSM cohorts, if the post-matching sample size still allows for a powered analysis, or IPTW cohorts if not. Using observed clinical events, we will calculate incidence rates and 95% confidence intervals for PSM (or IPTW) cohorts. We will estimate the hazard ratios and confidence intervals via Cox regression for our primary outcome (HHF). We will also estimate differences in healthcare utilization using incident counts, by performing either Poisson or negative binomial regression. Differences in cost outcomes will be assessed by generalized linear regression using a Gamma family link function. We will also explore instrumental variables that are employed to minimize residual confounding after PSM (or IPTW).	
Milestones:	The database for this analysis will be constructed by March 08, 2021, Data analyses will be complete April 12, 20201. A report of the findings from this study will be complete for review June 7, 2021.	

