9.1 STUDY DESIGN

This study will be a non-interventional study using existing data from January 1, 2014 to the date of the latest available data from an IQVIA (detailed below) database. Data available after March 31, 2020 will not be used due to the potential confounding events of coronavirus.

The study will analyze the clinical and economic effect of empagliflozin in Type 2 Diabetes (T2D) patients with Cardiovascular Disease (CVD). Empagliflozin initiators, as an add-on to metformin therapy comprise the treatment population. Patients initiating sulfonylureas as an add-on to metformin comprise the control population.

The index date for the empagliflozin add-on therapy arm is defined as the date of initiation of empagliflozin.

Treatment patient: Empagliflozin + Metformin
Control patient: Sulfonylurea + Metformin
 Metformin initiation Index Date = Empagliflozin/Sulfonlurea initiation

Page 16 of 36

The index date for the sulfonylurea add-on therapy control arm in a format parallel to the definition for the empagliflozin add-on therapy treatment arm, i.e., the index date is defined as the date of initiation of sulfonylurea therapy. We will control for exposure time in our propensity score calculations.

Baseline characteristics for all patients as well as their enrollment status will be confirmed using 12 months of claims data prior to the index date. Cardiovascular events, healthcare utilization, and its associated costs will be observed from the index date until the end of the study period. Outcomes and the associated costs will be monitored and then compared between cases and controls using inverse probability treatment weighting (IPTW), or, as sample size allows, propensity score matching.

*Monitoring period can also be ended by one of the events described in the data analysis section below

For this study, index date selection period will be from 01/01/2015 to 1/31/2020. Follow-up up period for patients not meeting any of the stopping criteria mentioned below will extend until 3/31/2020.

Finally, starting with the initiation of treatment, we observe patient outcomes until one of the following stopping criteria occur:

- discontinuation (defined as a gap in sulfonylurea, empagliflozin, or metformin of >30 days between fills) or switch or addition of a drug in the comparator and/or other antihyperglycemic agents class
- occurrence(s) of an outcome of interest
- nursing home admission
- healthcare plan disenrollment
- end of the study period

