9.2.2 Study population

Inclusion criteria:

- Prevalent metformin use + initiation of empagliflozin OR prevalent metformin use + initiation of a sulfonylurea
- ≥ 18 years of age at index date during study observation
- ≥1 inpatient and/or ≥ 2 outpatient claims denoting T2D diagnosis (in any position) in the 12 months prior to index date (Diagnosis codes available in the appendix Error! Reference source not found.)
- ≥1 inpatient and/or ≥2 outpatient claims denoting CVD (in any position) diagnosis in the 12 months prior to index date (Diagnosis codes available in the additional workbooks "ICD 9 Dx Codes.xlsx" and "ICD 10 Dx Codes.xlsx")
- ≥ 2 months post-index date
- ≥12 months of no exposure to T2D medications in the pre-index period (excluding metformin in both arms)
- ≥ 12 months of continuous enrollment prior to index date

Exclusion criteria:

- Diagnosis of Type 1 Diabetes, secondary, or gestational diabetes in the 12 months prior to index date (Diagnosis codes available in the additional workbooks "ICD 9 Dx Codes.xlsx" and "ICD 10 Dx Codes.xlsx"))
- Diagnosis of severe comorbidities including malignancy, end-stage renal disease, human immunodeficiency virus, Hepatitis C infection, or organ transplant in the 12 months prior to index date (Diagnosis codes available in the additional workbooks "ICD 9 Dx Codes.xlsx" and "ICD 10 Dx Codes.xlsx")
- Admission to nursing home in the 12 months prior to index date

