Stable angina; n (%)			
Other chronic ischemic heart disease; n (%)			
Previous coronary revascularization; n (%)			
Ischemic or hemorrhagic stroke; n (%)			
Ischemic stroke; n (%)			
Transient ischemic attack; n (%)			
	1	1	

Hemorrhagic stroke and other cerebrovascular disease; n $\binom{6}{3}$		
Late effects of cerebrovascular disease or procedure; n		
(%)		
Heart failure; n (%)		
Peripheral arterial disease or surgery; n (%)		
Atrial fibrillation; n (%)		
Other cardiac dysrhythmia; n (%)		
Other cardiovascular disease; n (%)		
Hypertension; n (%)		
Hyperlipidemia ; n (%)		
Edema; n (%)		
Non-diabetic renal dysfunction; n (%)		
Acute kidney injury; n (%)		
Chronic kidney disease; n (%)		
Chronic kidney disease stage 1-2; n (%)		
Chronic kidney disease stage 3+ or dialysis; n (%)		
Hypertensive nephropathy; n (%)		
Miscellaneous renal insufficiency ; n (%)		
Kidney or bladder stones; n (%)		
Urinary tract infections; n (%)		
COPD; n (%)		
Asthma; n (%)		
Obstructive sleep apnea; n (%)		
Pneumonia; n (%)		
Liver disease; n (%)		
Osteoarthritis; n (%)		
Other arthritis, arthropathies and musculoskeletal pain; n (%)		
Dorsopathies; n (%)		
Fractures; n (%)		
Falls; n (%)		
Osteoporosis; n (%)		
Disorders of thyroid gland; n (%)		
Depression; n (%)		
Anxiety; n (%)		
Sleep disorders; n (%)		
Dementia; n (%)		
Delirium; n (%)		
Psychosis; n (%)		
Angiotensin converting enzyme inhibitors; n (%)		
Angiotensin II receptor blockers; n (%)		

Beta-blockers; n (%)		
Calcium-channel blockers; n (%)		
Thiazide diuretics; n (%)		
Loop diuretics; n (%)		
Other diuretics; n (%)		
Nitrates; n (%)		
Other hypertension drugs; n (%)		
Digoxin; n (%)		
Anti-arrhythmics; n (%)		
COPD or asthma medications; n (%)		
Statins; n (%)		
Other lipid-lowering drugs; n (%)		
Antiplatelet agents; n (%)		
Oral anticoagulants; n (%)		
Heparin and other low-molecular weight heparins; n (%)		
Nonsteroidal anti-inflammatory drugs; n (%)		
Oral corticosteroids; n (%)		
Bisphosphonates; n (%)		
Opioids; n (%)		
Antidepressants; n (%)		
Antipsychotics; n (%)		
Anticonvulsants; n (%)		
Benzodiazepines; n (%)		
Other anxiolytics or hypnotics; n (%)		
Dementia medications; n (%)		
Antiparkinsonian medications; n (%)		
Hospitalization within prior 30 days; n (%)		
Hospitalization during prior 31-365 days; n (%)		
No. hospitalizations; mean (sd)		
No. hospital days; mean (sd)		
No. emergency department visits; mean (sd)		
No. office visits; mean (sd)		

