Endocrinologist visit within prior 30 days; n (%)		
Endocrinologist visit during prior 31-365 days; n (%)		
No. endocrinologist visits; mean (sd)		
Internal medicine visit within prior 30 days; n (%)		
Internal medicine visit during prior 31-365 days; n (%)		
No. internal medicine visits; mean (sd)		
Cardiologist visit within prior 30 days; n (%)		
Cardiologist visit during prior 31-365 days; n (%)		

No. cardiologist visits; mean (sd)	
Electrocardiogram; n (%)	
No. electrocardiograms, mean (sd)	
No. distinct medication prescriptions; mean (sd)	
Use of glucose test strips; n (%)	
No. HbA1c tests ordered; mean (sd)	
No. glucose tests ordered; mean (sd)	
No. microalbuminuria tests ordered; mean (sd)	
No. creatinine tests ordered; mean (sd)	
No. BUN tests ordered, mean (sd)	
No. lipid tests; mean (sd)	

The table above shows our complete set of baseline characteristics. All comorbidities and previous acute conditions and previous utilization in the previous 12 months will be recorded. Age at index date will be calculated as the time difference between the index date and the patient's birth date. Identification of comorbidities and previous utilization will follow the following rules:

- Chronic comorbidities and previous acute conditions will be identified by occurrence of at least one ICD 9/10 for the respective condition in any position. See the additional workbooks titled "ICD 9 Dx Codes.xlsx" and "ICD 10 Dx Codes.xlsx" for a detailed list of ICD 9/10 codes that identify comorbidities.
- Previous healthcare utilization will be identified by occurrence of CPT or HCPCS codes for the respective form of utilization. See the additional workbooks "CPT codes.xlsx" and "HCSPCS codes.xlsx" for a detailed list of CPT and HCPCS codes.
- Previous prescription medications will be identified by occurrence of prescription filling with a medication's respective NDC or HCSPCS code. See additional workbook "NDC codes.xlsx" and "HCSPCS codes.xlsx" for a detailed list of relevant codes.

Also, given that we are comparing a branded agent against generic agent, we will perform exploratory instrumental variable analysis, in order to account for the confounding by indication. Some example of instrumental variables we can use and will explore the appropriateness of are:

- First three digits of zip code (ZIP3) and/or State
- National Provider Identifier (NPI)
- Index date and/or index quarter

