9.3.2.2 Secondary outcomes

Secondary outcomes

- Healthcare utilization outcomes: hospitalizations, emergency department (ED) visits, length of stay, number of filled drugs, outpatient visits
- All cause cost: Total cost of care, divided by medical (inpatient costs, outpatient costs, emergency costs) and pharmacy costs (all reported in Per Patient Per Month (PPPM) costs)

Exploratory outcomes

• Effectiveness outcomes: 2-point MACE as a Composite Score of myocardial infarction, stroke or coronary revascularization

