The nearest neighbor and K-nearest neighbor algorithms are typically implemented without replacement, meaning that when control candidate i has been selected as a match for case member 1, he/she is no longer available as a match candidate for case member 2. In this arrangement, the order in which the matching is implemented across patients will affect the quality of the overall match. For example, if individuals are first ranked by age, a slightly different result will be obtained than if individuals are first ranked by decreasing propensity score.

The study team will select a specific propensity score matching method following a thorough inspection of the analytic dataset. If the sample sizes for cases and controls are large enough we will consider using nearest neighbor with caliper matching. If this is not the case or if this approach fails to find a match for a large number of empagliflozin add-on patients (>10% of the cases fail to match), we will loosen the caliper width to up to 0.6 (where bias reduction is still up to >90%). Alternatively, if we are unable to find a good match for over 10% of the cases even after loosening the caliper width to 0.6, we will consider using matching with replacement. If we are still unable to match an acceptable number of cases, we will implement inverse probability of treatment weighting (IPTW), which allows for complete inclusion of the cases.

Following the International Society for Pharmacoeconomics and Outcomes Research (ISPOR) best practices, [70] as a validation measure we will examine whether there are large differences in observed attributes (covariate values) of the empagliflozin add-on patients and the reweighted control group by assessing visual tools, such as density balance plots, and standardized mean differences. We will determine that the covariates are well-balanced if standardized mean differences do not exceed 10%. These analyses will serve as tools for assessing the quality of the matching procedure.

Step 2: Calculate descriptive statistics

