We will then use our matched cohorts to calculate descriptive statistics of the baseline characteristics of our patient population (separately for the empagliflozin cohort, the sulfonylurea cohort, and the overall population). After calculation of standardized mean differences, chi-square tests will be used to assess statistically significant differences for categorical variables, and t-tests will be used to assess statistically significant differences for continuous variables.

Step 3: Construct statistical models of primary and secondary outcomes

Using observed safety and effectiveness events, we will calculate incidence rates and 95% confidence intervals for IPTW/PSM matched cohorts. We will estimate the hazard ratios and confidence intervals via Cox regression for primary outcome of interest, comparing empagliflozin vs. comparison group. We will also estimate differences in healthcare utilization using incident counts, by performing either Poisson or negative binomial regression, and differences in cost outcomes will be assessed by generalized linear regression using a Gamma family log link function.

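### Pre-index cost is missing from the covariate table that feeds the propensity score and balance check, although PPPM cost is a secondary outcome

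*Protocol*

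**What the plan says.** - Protocol 9.3.2.2 lists the secondary cost outcomes: "All cause cost: Total cost of care, divided by medical (inpatient costs, outpatient costs, emergency costs) and pharmacy costs", reported PPPM.
- Protocol 9.7.1, Step 3 gives the cost model: "differences in cost outcomes will be assessed by generalized linear regression using a Gamma family log link function". No covariates are named for this model or for any other in Step 3.
- The Abstract ties the propensity score to a list: "Propensity scores will be calculated using the listed covariates (below) and used to construct PSM cohorts", with IPTW as the fallback.
- Section 9.3 closes that list: "The table above shows our complete set of baseline characteristics".
- The balance rule in 9.7.1, Step 1 applies to the same covariates: "We will determine that the covariates are well-balanced if standardized mean differences do not exceed 10" (per cent).
- The baseline period is covered by claims. Section 9.1 says "Baseline characteristics for all patients as well as their enrollment status will be confirmed using 12 months of claims data prior to the index date", and 9.2.2 requires at least "12 months of continuous enrollment prior to index date".

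**The concern.** For a cost outcome, the same patient's cost before index is the direct baseline measure. The protocol holds a full year of claims on everyone, yet its covariate table has no cost row, and section 9.1 speaks of costs only from the index date onward. Two things follow if the plan is carried out as written.

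- Patients are not matched or weighted on prior cost, and the balance table cannot reveal a difference in it. Any such difference would be read as part of the treatment effect on cost.
- Unless prior cost enters the cost model, variance that it could explain stays in the comparison.

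What is at stake is the economic objective, which is in the study title. The heart failure comparison does not depend on it.

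**Working it through.** **1. Is cost really absent?** Reading the 9.3 table row by row gives demographics, entry quarter, comorbidities and a comorbidity score, diabetes complications and drugs, lifestyle factors, 28 non-diabetes drug-class flags, and counts of admissions, hospital days, emergency and office visits, specialist visits, distinct prescriptions and tests. There is no total, medical or pharmacy cost. The shorter covariate list in the Abstract has none either.

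**2. Can it be derived?** Section 9.4 does not list paid amounts among its example data points. However, the source is an adjudicated claims database, and the same fields must supply the post-index cost outcome. With 12 months of required enrollment, the baseline value is available for every patient. This is an inference, but a safe one.

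**3. Do the proxies cover it?** Partly. Hospital days reflect inpatient intensity, and the drug-class flags reflect case mix. None carries a price. A class flag or a count of distinct prescriptions treats a cheap and an expensive product alike, so pharmacy spend is the least well covered.

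**4. Size.** The protocol states no cost figure to reproduce. Its powered figures (169 to 470 events) concern heart failure hospitalization only. The cost SD, pre/post correlation and imbalance below are all assumed.

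*Precision with no proxies in the model.* The ratio of confidence interval widths is √(1 − ρ²), where ρ is the pre/post correlation.

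| ρ | Width ratio | Equivalent gain in sample, 1/(1 − ρ²) − 1 |
|---|---|---|
| 0.3 | 0.95 | 10% |
| 0.5 | 0.87 | 33% |
| 0.7 | 0.71 | 96% |

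*Precision beyond the proxies.* If the listed proxies were already in the cost model, the ratio is √[(1 − R²full)/(1 − R²proxy)]. Assume the proxies explain 10% to 30% of variance and baseline cost adds 5 to 20 percentage points:

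- smallest gain: √(0.85/0.90) = 0.97
- largest gain: √(0.50/0.70) = 0.85

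*Imbalance.* With log-cost SD 1, a residual baseline difference of d SD and no true effect, the expected cost ratio is exp(ρ × d).

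| d | ρ = 0.3 | ρ = 0.5 | ρ = 0.7 |
|---|---|---|---|
| 0.1 | 1.03 | 1.05 | 1.07 |
| 0.2 | 1.06 | 1.11 | 1.15 |

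A simulated Gamma log-link model agrees. It used 1,968 per arm, which is the sum of the empagliflozin rows with any metformin in 9.5 (461 + 331 + 375 + 801), and 200 runs per setting. The unadjusted ratios were 1.027, 1.047 and 1.074 at d = 0.1, and 1.055, 1.105 and 1.151 at d = 0.2. With baseline cost in the model they lay between 0.995 and 1.001.

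That full correction is the best case, because the imbalance was in the adjusted variable itself. In a separate simulation the 0.1 SD imbalance sat in an underlying cost level that pre-index cost only partly captures. Adjustment then moved the ratio from 1.060 to 1.032 and the false rejection rate from 23% to 11%, so it reduced the bias without removing it.

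**5. What each part of the fix does.** A difference of 0.1 SD sits at the protocol's own 10% limit and would pass even if cost were listed. Listing cost guards against larger differences. Only the model term addresses those within tolerance.

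**The case against.** The strongest reply has four parts.

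- **Model covariates belong in the analysis plan.** Step 3 names the family and link and is silent on covariates, and section 6 schedules the analysis plan for after the protocol date. A reader might infer that the protocol excludes baseline cost from the cost model. It does not. This stands, so the model term is a recommendation and not the correction of a stated exclusion. It does not answer the point about the covariate table, which the protocol does fix.
- **The proxies are extensive, and prior diabetes drugs other than metformin are ruled out in both arms by 9.2.2.** Earlier spending on other branded diabetes drugs is therefore nil by design. This stands and lowers the likely imbalance. Spending on other drugs and medical care can still differ.
- **The word complete is not literal.** The Abstract adds length of metformin use and 9.1 adds exposure time, neither of which has a row in the table, and the entry quarters stop at Q3 2015 although indexing runs to January 2020. This is fair, but neither addition is a cost.
- **Any size is set by assumption.** A reader might take the $412 monthly difference in section 7, assume ρ = 0.5 and an SD of $4,000 to $6,000, and conclude that 6 to 12 points of power are lost. The documents do not support this. The $412 is against other branded agents and not sulfonylureas, the SD and ρ are not given, 1:1 matching is not settled, and 9.5 says the sample will change. Dollar estimates of bias fail for the same reasons.

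**Conclusion.** The point holds for the covariate table. As written, pre-index cost is neither balanced by design nor examined afterwards, although it is the baseline value of a named secondary outcome and is available for everyone. The existing proxies soften the problem but do not measure price or spend.

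Its size is unknown. The figures above are illustrative and rest on assumed correlations of 0.3 to 0.7 and imbalances of 0.1 to 0.2 SD. What matters is the correlation that remains after the proxies, and the gain may be small. It would go too far to say that the cost comparison is shown to be biased, or that adding prior cost would remove confounding. The conclusion is limited to the secondary cost outcomes.

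**What to change.** - In 9.3, add 12-month pre-index total, medical and pharmacy PPPM cost to the covariate table, so that they enter the propensity score and the standardized-difference check.
- In 9.7.1, Step 3, include the corresponding log-transformed baseline cost in each cost model, with a stated way of handling zeros, for example log(cost + 1). With a log link the cost ratio is collapsible, so this adjustment does not in itself change what is estimated.
- Describe the purpose as reducing residual imbalance and variance, not as removing confounding.

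The cost is a few derived variables from claims already held and a sentence in each section. No new data or patients are needed. The small downside is a few more propensity score terms, which could leave slightly more empagliflozin patients unmatched.

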9.3 VARIABLES

Exposure cohorts

Treatment with empagliflozin (as add-on therapy with metformin)

• Treatment with a sulfonylurea (as add-on therapy with metformin) Exposure will be identified by recorded prescription filling matching the NDC codes for empagliflozin or sulfonylurea, respectively. See list of identifying NDC codes in the additional workbook titled "NDC Codes.xlsx".

Covariates

Covariates included will be those previously published in the literature.

Baseline characteristics	Metformin + Sulfonylureas (N =)	Metformin + Empagliflozin (N =)	St. Diff.
Age; mean (sd)			
Age categories			
18 - 54; n (%)			
55 - 64; n (%)			
65 - 74; n (%)			
>= 75; n (%)			
Male; n (%)			
Race			
White; n (%)			
Black; n (%)			
Asian; n (%)			
Hispanic; n (%)			
North American Native; n (%)			
Other/Unknown; n (%)			
Region			
Northeast; n (%)			
South; n (%)			
Midwest; n (%)			
West; n (%)			
Quarter and year of cohort entry			
Q3 2014; n (%)			
Q4 2014; n (%)			
Q1 2015; n (%)			
Q2 2015; n (%)			
Q3 2015; n (%)			
Combined comorbidity score; mean (sd)			
No. distinct diagnoses; mean (sd)			
Diabetic nephropathy; n (%)			
Diabetic retinopathy; n (%)			
Diabetes with other ophthalmic conditions or ophtalmic procedures; n (%)			
Diabetic neuropathy; n (%)			
Diabetes with peripheral circulatory disorders; n (%)			

001-MCS-90-118_RD-23 (1.0) / Saved on: 25 Nov 2019

Diabetic Foot: n (%)			
Lower extremity amputation: n (%)			
Skin infections: p (%)			
Skill infections, $n(70)$			
Foot ulcer; n (%)			
Erectile dysfunction; n (%)			
Hypoglycemia ; n (%)			
Hyperglycemia; n (%)			
(%)			
Diabetic ketoacidosis; n (%)			
Hyperosmolar hyperglycemic nonketotic syndrome; n (%)			
Diabetes with unspecified complication; n (%)			
Naive new user; n (%)			
Monotherapy; n (%)			
Dual therapy with metformin; n (%)			
Concomitant initiation or current use of metformin; n (%)			
Concomitant initiation or current use of sulfonylureas; n (%)			
Past use of metformin; n (%)			
Past use of sulfonylureas; n (%)			
Past use of insulin; n (%)			
Past use of GLP-1 RAs; n (%)			
Past use of glitazones; n (%)			
Any use of meglitinides; n (%)			
Any use of alpha-glucosidase inhibitors; n (%)			
Lifestyle factors			
Obesity; n (%)			
Overweight; n (%)			
Smoking; n (%)			
Alcohol abuse or dependence; n (%)			
Drug abuse or dependence; n (%)			
Ischemic heart disease; n (%)			
Acute myocardial infarction; n (%)			
Old myocardial infarction; n (%)			
Unstable angina; n (%)			

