9.3.2 Outcomes

9.3.2.1 Primary outcomes

Primary outcome

• First hospitalization for congestive heart failure (HHF) (we will first analyze this by looking at diagnosis code in any position, we will then run the analysis considering diagnosis coding in either the principal or secondary position).

The primary scope of the analysis will be limited to the primary outcome (hospitalization for HF), for which the study will be powered for, and limited to HCRU and cost outcomes. For all exploratory effectiveness outcomes outlined above, we will first examine the number of events, and incidence rate of the events in the follow-up for the unmatched cohort, before performing the final analysis, to evaluate feasibility of inclusion of these exploratory outcomes.

Clinical outcomes will be identified by occurrence of a combination of the ICD 9/10 for the respective condition and HCSPCS code. See additional workbooks "ICD 9 Dx Codes.xlsx" and "ICD 10 Dx Codes.xlsx" and "HCPSC codes.xlsx" for a detailed list of relevant ICD 9/10 codes and HCSPCS codes, respectively.

Effectiveness Outcome	Metformin + Sulfonylurea(IR)	Metformin + Empagliflozin (IR)	Hazard Ratio (95% CI)
HHF			
MACE			
Myocardial infarction			
Stroke			
Coronary revascularization			
All-cause death			

See sample results for the propensity score-matched population below:

Utilization Outcome (12 months post index date)	Metformin + Sulfonylurea (IR)	Metformin + Empagliflozin (IR)	Coefficient (95% CI)	P value
Hospitalizations				
LOS				
ED visits				
Outpatient visits				
Drug orders				
Total care costs				
Medical costs				

Pharmacy costs		
2		

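### The one-part Gamma cost model is applied to inpatient and emergency costs with no rule for zero-cost patients, and the 12-month results heading does not match the variable follow-up

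*Protocol*

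**What the plan says.** Protocol section 9.7.1 (Step 3) assigns one model to all cost outcomes: "differences in cost outcomes will be assessed by generalized linear regression using a Gamma family log link function". The abstract (section 4) does the same without naming the link: "Differences in cost outcomes will be assessed by generalized linear regression using a Gamma family link function". Section 9.3.2.2 breaks total cost into "medical (inpatient costs, outpatient costs, emergency costs) and pharmacy costs (all reported in Per Patient Per Month (PPPM) costs". No second model part, rule for zeros or software is given.

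The sample results table in section 9.3.2.1 is headed "Utilization Outcome (12 months post index date". Its cost rows are total, medical and pharmacy, with no separate inpatient or emergency cost row.

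Follow-up is variable. Section 9.2.2 asks for "≥ 2 months post-index date". Section 9.1 ends observation at, among other events, "discontinuation (defined as a gap in sulfonylurea, empagliflozin, or metformin of >30 days between fills", and otherwise runs to 3/31/2020. Utilization is compared separately by Poisson or negative binomial regression (section 9.7.1).

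**The concern.** Inpatient and emergency costs are zero for every patient without an admission or emergency visit. A Gamma distribution does not admit zero, so the named model does not fit these components as it stands. An analyst whose software rejects the records may be led to drop them. The comparison would then be of cost per hospitalised patient, which cannot show a saving that comes from fewer patients being hospitalised. That choice should be fixed before results are seen.

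Two related points concern follow-up time. A heading that fixes 12 months sits badly with follow-up that stops at discontinuation or at a calendar date. Counts over a nominal 12 months would mix persistence with utilization. Cost per patient per month can also mean two different quantities, depending on whether patients or person-months carry equal weight.

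**Working it through.** The protocol gives no cost figure, zero-cost share or all-cause admission rate, so there is no stated figure to reproduce. All rates below are assumptions.

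**1. How many zeros?** With a constant admission rate r per patient-year and follow-up t, the share with no admission is exp(−r·t). At r = 0.3 and one year, exp(−0.3) = 0.74.

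| Assumed rate per year | 2 months | 1 year | 2 years |
|---|---|---|---|
| 0.1 | 98% | 90% | 82% |
| 0.3 | 95% | 74% | 55% |
| 0.5 | 92% | 61% | 37% |
| 1.0 | 85% | 37% | 14% |

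Zeros will occur. Their share depends on inputs that the protocol does not give. Emergency visits follow the same formula at their own rate.

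**2. What a Gamma model does with a zero.** The Gamma log-density contains (k − 1)·log(y), where k is the shape. At y = 0 it is +∞ for k = 0.5, finite at k = 1 and −∞ for k = 2, so a full-likelihood fit breaks down. In R 4.3.3, glm with the Gamma family stops because non-positive values are not allowed.

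The estimating equations behave differently. With a log link they are Σ x(y − μ)μ/V(μ) = 0, which need μ > 0 but not y > 0. With treatment as the only covariate, μ is constant within an arm and the solution is the arm mean, zeros included, whether V is μ or μ².

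**3. Effect of keeping or dropping zeros.** Assume 20% of controls and 15% of empagliflozin patients hospitalised, with the same mean cost c per hospitalised patient.
- True ratio of means: 0.15c / 0.20c = 0.75.
- Users only: c / c = 1.00.
- Expected share of zeros with equal arms: 1 − (0.20 + 0.15)/2 = 82.5%.

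One simulated data set with 20,000 per arm (82.6% zeros) gave:
- Gamma/log, all records: 0.725, robust SE of the log ratio 0.0333.
- Quasi-Poisson/log, all records: 0.725, robust SE 0.0333.
- Gamma/log, positive costs only: 1.002.

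The value 0.725 is that sample's ratio of means and lies about one SE from 0.75: log(0.725/0.75) = −0.034.

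A second simulation used 1,600 per arm, 300 repeats per scenario, control admission probability from 5% to 60%, and a true ratio of 0.65. Gamma/log with zeros kept averaged 0.65 to 0.66, with robust 95% interval coverage of 92% to 96%. Users only averaged about 1.00. In one such data set fitted in R, quasi-likelihood with V = μ² gave 0.631, equal to the ratio of arm means, and users only gave 0.930.

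**4. The 12-month heading.** Section 9.1 allows index dates from 01/01/2015 to 1/31/2020, which is 61 months, and ends follow-up on 3/31/2020. Patients indexed from April 2019 to January 2020 (10 of the 61 months) cannot reach 12 months even with perfect persistence. On-treatment stopping shortens follow-up for others.

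**5. Weighting of per-month cost.** For one arm with costs y, months t and mean t·e^β (a log(t) offset):
- Gamma, V = μ²: Σ(y − μ)/μ = 0 gives e^β = (1/n)Σ(y/t), the unweighted average of patient-level monthly costs.
- Poisson-type, V = μ: Σ(y − μ) = 0 gives e^β = Σy/Σt, cost per person-month.

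A simulated comparison agreed: Gamma/log gave a ratio of 1.105 both for unweighted per-month cost and with the offset, against 1.053 for the person-time-weighted ratio. The size of that gap is specific to the simulated data and is not an estimate for this study.

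**The case against.** A reader might infer that the planned model must either fail or compare only users, so that the study will miss savings from avoided admissions. The documents do not support that. Nothing in the protocol says that zero-cost patients will be excluded. Step 3 of the working shows that Gamma/log on all records, with a robust standard error, gives the same answer as quasi-Poisson. The loss comes from dropping records, not from the Gamma family. The 1.00 is also built into the illustration, because cost per user was assumed equal.

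A reader might also take it that these costs are zero for most patients. That is plausible with short follow-up, but no figure in the protocol establishes it, and the table in step 1 runs from 14% to 98%.

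Other planned analyses keep the benefit visible. Section 9.3 states that "Exposure will be identified by recorded prescription filling matching the NDC codes for empagliflozin or sulfonylurea, respectively", so each patient has at least one fill. If the index fill is costed, pharmacy and total cost should be positive for everyone. Avoided admissions therefore enter total cost, and they also enter the count regressions, which keep zeros.

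Finally, section 6 schedules a separate analysis plan, which may say how zeros are handled, and the sample table's arm columns are labelled as incidence rates, so raw counts are not necessarily intended. Both points stand and limit the concern. They do not remove it: the protocol goes beyond silence by naming a distribution that excludes zero for components that contain zeros, and the table heading conflicts with section 9.1 as written.

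**Conclusion.** The point holds in a limited form. The one-part Gamma/log model does not fit inpatient and emergency costs as stated, and medical or outpatient cost could hold a few zeros as well. Whether this matters depends on an unstated choice. With zeros kept and robust standard errors, the mean ratio is correct. With zeros dropped, a ratio of 0.75 would be reported as 1.00 under the assumed 20% versus 15% hospitalised and equal cost per user. Total cost, admission counts and the primary outcome are not affected by the zeros.

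The 12-month heading is a separate inconsistency with the variable, on-treatment follow-up. On cost per month, it would be tempting to add a log(person-months) offset and keep Gamma. Step 5 shows that this leaves short and long follow-up equally weighted, so the offset alone does not deliver cost per person-month.

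**What to change.** - **Component costs.** For inpatient, emergency and any other component with zeros, state that all patients are kept. Use a log-link quasi-likelihood model (for example quasi-Poisson) with robust standard errors. Alternatively, use a two-part model (logistic for any cost, Gamma/log for positive cost) reported as the combined mean with a bootstrap confidence interval.
- **Utilization.** Reconcile the 12-month heading in section 9.3.2.1 with the follow-up in section 9.1, and model counts with a log(person-time) offset.
- **Cost per month.** State which quantity is meant. If it is cost per person-month of follow-up, use a Poisson-type variance with a log(person-months) offset, or weight by person-months.

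The cost is a few sentences and minor programming. The two-part result is slightly harder to present; the quasi-likelihood model avoids that.
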